3 INVESTIGATIONAL PLAN

3.1 Overall Study Design

This is a prospective, open-label, non-comparative, multi-centre, international, without direct individual benefit study, assessing the potential absorption of elemental impurities after chronic administration of Smecta® in subjects with chronic functional diarrhoea. It is intended that a total of 35 subjects will be enrolled (i.e. assigned to a treatment, please see section 4.1) to ensure that at least 29 subjects will complete the study. It is planned to have at least 40% of each gender in the entire study.

After a screening period of up to 6 weeks including a baseline assessment, each subject will be dosed with Smecta® TID over 5 weeks (Day 1 to Day 35) and then continue to be monitored over a post-treatment follow-up period of 3 months until end-of-study visit (see Figure 1). Blood samples, urine collections and faecessampling will be obtained at screening phase and baseline visit, over the treatment period and then during follow-up period. Potential adverse events will be collected and monitored throughout the study.

No formal interim analysis is planned during the study. However, BLL obtained on screening and baseline (prior the first intake of Investigational Medicine Product (IMP)) and during the study will be analysed and reviewed on an ongoing basis by the Sponsor for potential study adjustments (e.g.: confirm assumptions for sample size calculation).

[figure not shown]

Figure 1 Study Design and Visits

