4.6 Discontinuation of an Individual Subject

4.6.1 Discontinuation / Withdrawal Criteria

All subjects are free to interrupt or withdraw their consent to participate in the study at any time, for any reason, specified or non-specified, and without penalty.

CONFIDENTIAL – Protocol n°: D-FR-00250-108 v.4.0 Date: 07-SEPT-2016

A subject may also be discontinued from the study upon Sponsor's and/or Investigator's decision for any appropriate reason, such as safety related to an adverse event or concomitant therapy, major protocol violation or deviation, noncompliance with protocol restrictions, etc. Due to the study primary objective it is important that subjects participating to the study comply with the full treatment and follow-up schedule. Hence their wish to take part to the study up to its end should be fully discussed and confirmed at study entry. This requirement is to ensure the study scientific value by ensuring the collection of the full set of data necessary for its analysis and does not preclude any subject right to withdraw at any time as stated above.

All cases of discontinuation will be discussed between the Investigator and the Sponsor or its representative.

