4.6.3 Replacement Strategy

No replacement of subjects is foreseen in the study.

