8.1.2 Determination of Sample Size

The critical limit of $50\mu g/l$ of lead is chosen as being the most conservative value taken among various guidelines (risk of saturnism, observations under high lead exposure at work). The baseline blood lead concentration of $31,4\mu g/l$ is considered as being a mean blood lead concentration in a survey of 1949 adults (18-74 years old) living in France in 2006-2007 (Falq et al. 2011). This population is representative of the French population including different socio-demographic characteristics and environment risk factors such as: sex, age, smoking status, type of drinking water, leisure activities, age of housing, shellfish/crustacean consumption. Considering the inclusion and exclusion criteria defined for the study, the enrolled subjects should have BLL levels in the same range as reported in the survey.

With a standard error to the mean of [0,56], the mean blood lead concentration of 31.4 μ g/l is at confidence 95% to be found within [29.82; 32.98] under similar conditions. The non-superiority Δ margin is a clinical choice calculated as the difference of: $50 - 31.4 = 18.6 \mu$ g/l. A precision of 15% (CV) of the bioanalytical assay has been considered in the determination of sample size.

Based on the above considerations, a sample size of 29 subjects with baseline mean blood lead concentration no greater than 36 μ g/l (<36 μ g/l), is required to provide 81% power to reject the null hypothesis of a difference of means no greater than 18,6 μ g/l (\leq 18,6 μ g/l considered as no difference of means).

Considering potential drop-out, it is planned to enrol a total of 35 subjects to ensure that at least 29 subjects completed the study.

Subjects who prematurely discontinue after IMP administration will not be replaced.

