3.2.2 Biological and clinical evaluations

3.2.2.1 Biological evaluations

Biological evaluations concern blood samples for elemental impurities, urine collection (24-hour) for elemental impurities.

The baseline for blood concentrations (lead and other elemental impurities) will be the average between the available screening and pre-dose (Day-1) values (as defined in [Appendix 1 \(5\)](#)).

For blood lead concentrations, absolute values and changes (as defined in [Appendix 1 \(6\)](#)) from BLL baseline will be summarized for all post-baseline time-points on the ITT and the PP population.

Additionally, for all follow-up time points, absolute changes from D36 (in the morning) will be calculated and summarized.

Corresponding listings will be provided on ITT population.

Plots of mean absolute changes over time (with 95% confidence interval) will be provided on ITT and PP population and individual corresponding plots on ITT population (one graph for full profile). For blood lead concentrations, same analyses by country will be presented.

For other elemental impurities blood concentrations, the analysis will also be described in the same way as for blood lead concentrations expect for plots of means and individual corresponding plots which will be provided only for arsenic and barium parameters.

The baseline for urine concentrations (lead and other elemental impurities) and Ae parameter will be defined as the last available (and reliable if applicable) assessment collected prior to receiving dose of Smecta® on Day 1.

For urine lead concentrations and other elemental impurities, the same approach for blood lead concentrations will be done expect that there will be no plots.

The cumulative amount of EI (Elemental Impurities) excreted in urine (the Ae parameter) will be calculated (as defined in [Appendix 1 \(7\)](#)) and summarized at each scheduled assessment with absolute changes from baseline and absolute changes from D36 (in the morning) and listed on ITT population. Plot of mean of this cumulative amount (with 95% confidence interval) will be provided on ITT population if the number of data above the limit of quantification is sufficient.

The volume of urine will be only listed on ITT population.

For summary statistics, the following will be presented: n, arithmetic mean with its 95% confidence interval, standard deviation (SD), median and the range (minimum, maximum).

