3.2.3.6 Pregnancy tests

A listing with the date of examination, the status of the examination (done/not done/not applicable) and the result (positive/negative) will be provided by subject, timepoint, examination date and method: (serum on screening only or urine).

3.2.4 *Missing data and outliers*

3.2.4.1 *Missing data*

No missing value will be imputed.

If a value required a retest, the last reliable non-missing value will be taken into account if measured before the administration of Smecta®; and the first non-missing reliable value for post-baseline assessments. An assessment will be considered reliable if it is performed without any technical problem and if the result is within the range of plausible values.

Any repeat or additional assessments performed will be included in the individual subject data listings.

If there is a significant number of missing values for a subject (or if there is confirmed data appearing spurious), a decision will be made following consultation with the sponsor regarding the handling of these data in summaries, prior to database freeze and will be documented in the minutes of the data review.

3.2.4.2 *Missing or incomplete dates*

In all listings, missing or incomplete dates should be left as they have been recorded. However, for calculation / sorting / assignation based on dates, the following methods will be used:

The most conservative approach will be systematically considered (i.e. if the onset date of an AE is missing / incomplete, it is assumed to have occurred during the study treatment phase (e.g. a TEAE for AEs) except if the partial onset date or other data [stop date, ...] indicates differently).

A missing/incomplete date of medical history or disease diagnosis will be assumed to have occurred before any study treatment.

If a partial date and the associated information do not allow to state about the assignation to a group / category, all the possible groups / categories will be considered (e.g. a medication with partial start and stop dates could be considered as prior and concomitant treatment).

Where this is possible, the derivations based on a partial date will be presented as superior inequalities (e.g. for an AE started in 2004-02 after the administration performed on 2004-01-31, the days since last dose will be “ ≥ 2 ”, similarly the duration of ongoing AEs or medication will be “ $\geq xx$ ” according to the start and last visit dates).

3.2.4.3 *Outliers*

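### Blood-lead change is summarised on observed cases only: no planned analysis uses drop-outs' earlier values, and the early-discontinuation sample has no assigned time point

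*SAP*

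**What the plan says.** **Analysis.** SAP 3.2.2.1 says that absolute BLL values and changes "from BLL baseline will be summarized for all post-baseline time-points on the ITT and the PP population". Means carry 95% confidence intervals and are plotted. Follow-up values are also expressed as change from the Day 36 morning sample. Modelling of lead is optional and left to a separate plan.

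**Missing data.** SAP 3.2.4.1: "No missing value will be imputed". For a subject with many missing values, the handling in summaries is to be agreed with the sponsor before database freeze; no rule is given. The only sensitivity analysis named for BLL excludes subjects with high baseline lead.

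**Populations.** ITT (SAP 2.5) needs one pre-dose and at least one post-dose BLL. PP (SAP 2.6) contains only subjects who completed the last follow-up visit without a major deviation.

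**Drop-out.** Protocol 8.1.2: "Considering potential drop-out, it is planned to enrol a total of 35 subjects to ensure that at least 29 subjects completed the study". Protocol 4.6.3: "No replacement of subjects is foreseen in the study". Protocol 4.6.2 directs treated drop-outs to the EoS/ED visit (Visit 10), and Protocol Attachment 1 schedules an elemental-impurity blood sample there. SAP 1.3.2.2 lists that sample as Day 125. Neither document says where it is tabulated when the visit takes place early.

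**Routes out.** Protocol 4.6.1: "A subject may also be discontinued from the study upon Sponsor's and/or Investigator's decision for any appropriate reason". Safety is among the examples. Under Protocol 3.1, BLL values obtained "during the study will be analysed and reviewed on an ongoing basis by the Sponsor", with study adjustments as the stated purpose.

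**The concern.** Each mean rests on whoever was sampled at that visit. If subjects leave, the ITT curve mixes change within subjects with change in who remains. If those who leave had larger early rises, the later means are too low and their confidence intervals cover less often than 95%. The error runs toward the reassuring answer in a study meant to detect absorption.

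PP cannot check this, because it consists of completers. The weekly samples on Days 8 to 29 carry the information needed to correct it, but no planned analysis uses them in that way.

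The early-discontinuation sample raises a second problem. If an on-treatment or just-off-treatment value is tabulated under Visit 10, it enters the Day 125 mean as though it came from about three months after the last dose.

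**Working it through.** **1. The plan's own drop-out figure.** 29 / (1 − 6/35) = 35, so the enrolment figure reproduces. 6/35 = 17.1% is the largest loss the plan allows for. It is counted to study completion (Day 125). A subject who leaves after Day 36 has the Day 35/36 values, so the loss there is between 0 and 17.1%.

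**2. Size of the bias in general.** Let f be the fraction missing at a visit and D the excess mean change in missing over observed subjects. Observed-case bias = −f × D. The documents give no D, so it is assumed here.

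| D (µg/l) | f = 6/35 | f = 3/35 |
|---|---|---|
| 5 | −0.86 | −0.43 |
| 10 | −1.71 | −0.86 |
| 18.6 | −3.19 | −1.59 |

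**3. Selection on an earlier value.** Suppose the six leavers are the highest six of 35 on an earlier change that correlates r with the later one. With p = 6/35, z = 0.949 and φ(z) = 0.254, the mean of those remaining falls by r × 0.254 / (29/35) = 0.307 r SD. That is 0.307 × √29 = 1.65 r standard errors at n = 29: 0.8 SE at r = 0.5 and 1.3 SE at r = 0.8.

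**4. In µg/l.** Assumptions not in the documents: mean rise of 5 µg/l at Day 36; between-subject SD of the rise 3 to 10 µg/l; all six leave after Day 22. Taken from the protocol: 40-day half-life for the shape of rise and fall (relative to Day 36: 0.683 at Day 22, 0.583 at Day 65, 0.346 at Day 95, 0.206 at Day 125); noise SD 0.15 × 31.4 = 4.71 per sample; baseline the average of two samples.

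Formula check at Day 36:
- SD of rise 3: the SD of observed change is √(9 + 1.5 × 4.71²) = 6.50 and r = 0.43, so the bias is 0.307 × 0.43 × 6.50 = 0.86.
- SD of rise 10: 11.54 and 0.77 give 2.73.

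Simulation (35 subjects, eight visits, 3,000 runs per case; leavers chosen by highest Day 22 change, the rest at random):

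| SD of rise | Lead-related leavers | Bias Day 36 | Day 65 | Day 95 | Day 125 | CI coverage, Day 36 |
|---|---|---|---|---|---|---|
| 3 | 3 of 6 | −0.45 | −0.39 | −0.33 | −0.35 | 93% |
| 3 | 6 of 6 | −0.84 | −0.70 | −0.65 | −0.61 | 89% |
| 10 | 3 of 6 | −1.46 | −0.92 | −0.65 | −0.46 | 87% |
| 10 | 6 of 6 | −2.66 | −1.73 | −1.19 | −0.84 | 71% |

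Rounded outward, the range is about 0.3 to 2.8 µg/l. Against the margin: 0.3/18.6 = 2% and 2.8/18.6 = 15%. With no lead-related leavers, all biases are within simulation error of zero.

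**5. What a likelihood estimate does.** On the same data, the maximum-likelihood mean using Days 8 to 22 had bias within ±0.1 at every visit in every case, with a similar SD (Day 36, SD of rise 10, six lead-related: 2.10 against 2.08). With random drop-out nothing was lost (2.01 against 2.11).

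**6. A misplaced early-discontinuation sample.** Take six subjects leaving at Day 22 whose value is filed under Day 125. The expected rise is 5 × 0.683 = 3.4 instead of 5 × 0.206 = 1.0. With all 35 values in the mean, Day 125 moves up by 6/35 × 2.4 = 0.4 µg/l. The sign is opposite to that in step 4, so the two effects could mask each other.

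**The case against.** The case against is substantial, and much of it stands.

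- **Day 35/36.** A reader might infer that 17% of subjects lack a Day 35/36 value. The documents do not support this: the allowance runs to Day 125, and if all leavers go after Day 36 there is no Day 36 bias. Step 4 puts the whole loss early and is an upper case in that respect.
- **Follow-up BLL.** A reader might infer that drop-outs have no later BLL at all. Protocol 4.6.2 sends treated drop-outs to Visit 10, where BLL is sampled. The gap is the missing assignment rule.
- **Lead-driven withdrawal.** A reader might infer that subjects with rising lead will be withdrawn. There is no BLL withdrawal rule, nothing says that subjects or investigators are told on-study BLL, and the sponsor's review is for study adjustments such as checking sample-size assumptions. Together with discretionary discontinuation this leaves a possible route, no more.
- **The margin.** A reader might infer that drop-out could hide a mean rise of 18.6 µg/l. For an all-subject mean of 18.6, six leavers would need to average (18.6 − 29/35 × m) / (6/35), where m is the completers' mean: 108.5, 60.2 or 36.0 µg/l for m = 0, 10 or 15.
- **Existing displays.** Individual profiles, listings, n at each time point, subjects per visit and reasons for withdrawal are all planned, so leavers' trajectories can be seen. They do not give a corrected mean.
- **Descriptive study.** SAP 3.1.6 plans no test. The 95% intervals are still planned, and a shifted mean with a short interval misleads without a test.
- **The model's good performance.** Drop-out in the simulation depended only on observed values, which is the condition under which the likelihood method works. The near-zero bias is therefore largely built in and would not carry over to drop-out that depends on unobserved lead.

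**Conclusion.** The point holds in limited form. BLL change is analysed on observed cases, no pre-specified analysis uses drop-outs' earlier values, and the early-discontinuation sample has no assigned time point. Up to 17% of subjects may be absent by Day 125, and between 0 and 17% at Day 35/36.

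If leaving is related to lead already observed, later means are too low by about 0.3 to 2.8 µg/l. That rests on an assumed 5 µg/l rise, an assumed SD of the rise of 3 to 10 µg/l, and three to six lead-related leavers, all gone after Day 22. It is modest against the 18.6 µg/l margin, but 2.8 is 56% of the assumed 5 µg/l rise. If drop-out is unrelated to lead, the bias is zero. The documents establish neither case.

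This is a cheap improvement to the SAP. It does not show that the primary result will be wrong.

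**What to change.** In SAP 3.2.2.1, keep the descriptive tables and add:

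1. **One supporting analysis.** A likelihood-based repeated-measures model of BLL change on all ITT subjects, with visit and baseline BLL as fixed effects, over Days 8, 15, 22, 29, 36, 65, 95 and 125. Name one sample for Day 35/36: the Day 36 morning sample, which the SAP already uses as the reference for follow-up changes. Use an unstructured covariance and state a simpler fallback if it does not converge; eight visits need 8 × 9 / 2 = 36 covariance parameters from about 35 subjects.
2. **Reporting.** Give the model mean and 95% confidence interval at Days 36, 65, 95 and 125 beside the observed-case mean and its n.
3. **Early-discontinuation samples.** Analyse them by actual study day, with visit windows stated, and not as Day 125.
4. **One table.** Last observed BLL change for leavers and completers, so that lead-related leaving can be seen.

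The cost is SAP wording, one model and one or two tables, with no extra subjects, visits or samples. The downside is that the model assumes data are missing at random given the observed BLL values, which cannot be verified. That is why it supports the observed-case table and does not replace it.

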3.2.6 Withdrawals

Discontinued subjects will be listed and a summary table of the number and percentage of subjects who withdrew from the study and the reasons for withdrawal will be presented.

3.2.7 Demographic and baseline characteristics

All demographic (country, sex, race) and baseline characteristics (age, body height, body weight and BMI at baseline) as well as the substance use (alcohol, tobacco, caffeine and dietary habits use) will be listed by subject on the safety population.

Summary statistics will be provided for demographic and baseline characteristics as well as the substance use on the safety population.

For demographic and baseline characteristics, the results will be described by gender and by country.

The results of urine drug of abuse tests, alcohol breath test, post-menopausal status (at screening), and serology (at screening and Day-1) will only be provided in subjects data listings on the safety population by subject and examination date.

3.2.8 Medical and surgical history

Medical and surgical history will be coded using MedDRA Version 19.0 or higher.

Listings will present the primary system organ class, the preferred term and the reported term. The listings will be sorted by subject, start date, primary system organ class, preferred term and reported term on the safety population.

A frequency table of the number and percentage of subjects will be provided for all medical and surgical history by primary system organ class and preferred term for the safety population.

3.2.9 Subject compliance

The time and day of drug administration will be recorded by the study site when present at the clinical unit and by the subject when self-administered using a diary.

Compliance to diosmectite (Smecta®) intake will be based on this diary.

All treatment administration information will be listed by subject, timepoint and date of administration on the safety population.

Three listings will be performed: one for the treatments taken, one for the meals taken, and one for the drug accountability.

Study drug exposure (as defined in [Appendix 1 \(3\)](#)) in weeks will be summarized.

A summary table will present the global compliance (expressed in percentage as defined in [Appendix 1 \(4\)](#)) on the treatment period for the safety population.

Additionally, compliance will be categorized as follows: < 80% (Under compliance), 80-120% (Compliance) and > 120% (Over compliance) and will be summarized.

In the included population, protocol deviations from observed and scheduled times will be presented with the reasons for exclusion from the PP population.

All the protocol deviations identified will be also listed by subject with the reasons for exclusion.

A protocol deviation specification document will be provided further by Aepodia.

3.2.10 *Prior and concomitant medications*

Concomitant medication will be coded by using the World Health Organisation – Drug Dictionary (WHO-DD) June 2016 Version or higher.

The therapeutic class will correspond to the second level of anatomic therapeutic class (ATC) code, that is, corresponding to the first 3 figures.

The date and time of baseline (Smecta® on Day 1) will be used as the cut-off date for the definition of prior and concomitant medications:

A prior medication will be defined as a medication stopped prior to the date of baseline.

A concomitant medication will be defined as a medication which is taken by subject any time during the study after the date of baseline.

A medication that started before the date of baseline and is continuing after will be considered as both, prior and concomitant.

Prior, concomitant and both prior and concomitant medications will be flagged P, C and PC respectively, in all listings.

Listings will be presented for the therapeutic class, preferred name and reported name on the safety population. The listings will be sorted by subject, chronological start date, therapeutic class, preferred name and reported name.

Frequency tables of the number and percentage of subjects with at least one prior or, concomitant medication will be provided by therapeutic class and preferred name on the safety population.

3.2.11 *Prior medications for Chronic Diarrhoea*

Analysis of prior medications for chronic diarrhoea will be performed as described in section 3.2.10.

3.2.12 *Prior and concomitant non-drug therapies*

Prior and concomitant non-drug therapies will be coded using MedDRA Version 19.0 or higher. It will be listed by subject, chronological start date, primary system organ class, preferred term, and reported term.

3.2.13 *Concomitant surgical procedures*

Concomitant surgical procedures will be coded using MedDRA Version 19.0 or higher. It will be listed by subject, chronological start date, primary system organ class, preferred term, and reported term.

3.2.14 *Hospitalizations*

Dates of hospitalizations occurring during the study will be listed on included population with reported term, entry date, and discharge date.

3.2.15 *Derived data*

The derived data are variables which are calculated from the raw data in the electronic case report form (eCRF) and not included in the database and will be included in the listings.

3.2.16 *Rules and data formats*

Data will be presented using an appropriate number of decimal places (i.e. the number of decimal places used does not imply undue precision). Raw data will be presented with the number of decimal places collected, and derived data will be presented to an appropriate

number of decimal places. The appropriate number of decimal places will be determined by general practice, mathematical rationale or scientific rationale (e.g. age should be presented in whole numbers).

For summary statistics, the following will be presented: n, arithmetic mean, standard deviation (SD), median and the range (minimum, maximum).

Mean, median and standard deviation values will be reported with one decimal place greater than the raw/derived data that they summarise. Minimum and maximum values will be reported with the same precision as the raw data.

CV% and ratio will be presented with one decimal place.

Percentages will be reported with 1 decimal place and 0% will not be presented. Percentages will be calculated using a denominator of all subjects in a specified population. The denominator will be specified in a footnote to the tables for clarification if necessary.

All text fields must be left justified and numeric or numeric with some text specification (e.g. not done, unknown, < 4.5, ...) must be decimal justified. Dates will be presented in the format [yyyy-mm-dd] and times in the format [hh:mm].

